### **8.2.1 Analyses of Prevention Efficacy for HIV-1 Infections After the Week 80 Visit**

The primary analyses of prevention efficacy and the Cox model secondary analyses of prevention efficacy will be repeated including all MITT HIV-1 infections in the analysis occurring through to the Week 104 terminal study visit. These analyses are relevant because the right-tail of VRC01 concentration may be long enough that protection against infection could occur even against HIV-1 infections many weeks or months after the last VRC01 infusion.

## **8.3 Prevention Efficacy Against Measured Neutralization Sensitive Viruses**

### **8.3.1 Final Analyses Also Included in Interim Analyses**

For each primary HIV-1 infection endpoint, neutralization sensitivity of the majority breakthrough founding virus (and of other founding minor viral variants with frequency greater than 10%) at the first HIV-1 RNA positive time point to the VRC01 clinical lot is measured by three independent replicates of IC50 and IC80 from the TZM-bl target cell assay. (A ‘founder virus’ is an HIV-1 variant that is measured/observed based on sequencing the earliest available post-infection sample.) For each geometric mean readout (across the three replicates) of IC50 and IC80 separately, majority founder viruses are divided into five categories of sensitivity level (“sensitivity type”): Sensitive =  $< 0.3 \mu\text{g/mL}$ ; Moderately Sensitive =  $0.3\text{--}1 \mu\text{g/mL}$ ; Intermediate =  $1\text{--}3 \mu\text{g/mL}$ ; Moderately Resistant =  $3\text{--}10 \mu\text{g/mL}$ ; and Resistant =  $> 10 \mu\text{g/mL}$ . For infected cases with multiple assayed HIV-1 variants, the geometric mean IC50 and IC80 pertaining to the most sensitive variant is used for analysis. The report will include a table of the distributions of the number of HIV-1 infected cases (and/or assayed variants) by treatment assignment and sensitivity type, and boxplots of the distributions of geometric mean IC50 and IC80 readouts for infected cases by treatment assignment.

In addition, for each sensitivity type category, for IC50 and IC80 separately, the following results are presented:

- Estimated cumulative incidence curves of each HIV-1 sensitivity type by treatment assignment (Aalen-Johansen estimator)

- Estimated cumulative prevention efficacy curve for each HIV-1 sensitivity type (contrast of Aalen-Johansen estimates)
- Estimated proportional hazards prevention efficacy by quantitative  $\log_{10}$  IC50 or  $\log_{10}$  IC80 (method of Juraska and Gilbert (2013))

If the number of primary endpoint counts in some sensitivity type categories is small, then adjacent categories may be combined, to ensure at least 5 endpoints total per analyzed category.

### **8.3.2 Additional Analyses Included in the Final Analysis**

All of the primary and secondary analyses of overall prevention efficacy specified in Sections 8.1 and 8.2 will be repeated for the endpoint HIV-1 infection with sensitivity type Sensitive or Moderately Sensitive according to the definitions above. The statistical methods are the same, except cumulative incidence estimators are replaced with cause-specific cumulative incidence estimators and Cox model analyses right-censor primary HIV-1 infection endpoints of a different sensitivity type.

### **8.3.3 Prevention Efficacy Accounting for Number of Founding Viruses**

Another secondary analysis may be conducted to assess the effect of VRC01 on prevention of HIV-1 acquisition over 80 weeks using the method of Follmann and Huang (2015) that incorporates information on the number of HIV-1 founder viruses in HIV-1-infected participants. The method has increased efficiency relative to Cox proportional hazards regression if VRC01 reduces the number of founders.

## **8.4 Analysis of Exploratory Objective 1**

The use of oral FTC/TDF as PrEP will be assessed as described in Section 9.3.

## **8.5 Analysis of Exploratory Objective 2**

If there is substantial PrEP use detection at baseline, then the Cox model will be used to assess whether prevention efficacy significantly differs in subgroups with detectable versus undetectable baseline PrEP use, and to make inferences on prevention efficacy separately in each subgroup. In addition, if there is substantial PrEP use detected over the course of the study, then a marginal structural Cox model will be used to assess prevention efficacy in the sub-population not using PrEP.

More specifically, the primary analysis will be repeated where only MITT infection endpoints with no evidence of PrEP use at the time of HIV-1 diagnosis and at the time of the earliest evidence of infection will be included in the analysis. Intracellular TFV concentration (see Section 8.4) will be used to determine eligibility for this analysis. A participant is eligible if the TFV concentration is below the lower limit of detection as defined above at the diagnosis visit and at the visit with earliest evidence of HIV-1 infection (if different from the diagnosis visit). Since the ARVs are only detectable in plasma for roughly 14 days (Patterson et al. 2010) and some participants may have become infected before the 14-day window, with this approach we are not assured that all those included in the analysis were not using prophylactic ARVs at the time of infection. Therefore an additional analysis may be conducted that addresses this issue by also excluding participants from the HIV-1 acquisition analysis if they self-reported ARV use in the last 30 days at either the diagnosis visit or the last visit prior to diagnosis. These analyses will evaluate uninfected participants without accounting for data on their TFV concentrations.

## 8.6 Analysis of Exploratory Objective 3

Several analyses will make use of components of a 2-dimensional predicted HIV-1 risk score, which refers to identified best models predicting the conditional probability that a participant who is HIV-1-negative at  $t_0 = 0$  weeks becomes HIV-1-positive by a fixed time point  $t_1 = 80$  weeks (and  $t_1 = 104$  weeks) given a set of baseline input variables  $W$  and treatment stratum  $Z \in \{\text{control, pooled VRC01}\}$ .

The first step in the prediction problem involves, for each  $Z = z$  separately, estimating

$$\psi_{0,z}(W) = P_0(T \leq 80 \text{ weeks} \mid T > 0 \text{ weeks}, W, Z = z),$$

where  $T$  is a time from enrollment to the primary endpoint event (the parameter of interest for  $t_1 = 104$  weeks is defined analogously). It has been shown that this parameter is identifiable based on observed data in a trial with a time-to-event endpoint. The procedure for estimating  $\psi_{0,z}(W)$  is fully described in the “Statistical Analysis Plan for HIV-1 Risk Prediction in KwaZulu-Natal via Superlearner” developed by [name] and [name] (downloadable from <https://www.overleaf.com/read/bkycmxsdzzvm>), with all modifications described in the following paragraphs.

All estimators will be trained and applied separately in each AMP trial given major differences in demographics, risk behavior, and viral transmission and epidemiology between the two trial populations. Moreover, in the control-group risk prediction in HVTN 703/HPTN 081, two data sets will be used for training all estimators: Initially, we will restrict the training set to primary follow-up in HVTN 703/HPTN 081 control recipients only. Subsequently, we will enrich this training set by including 80 weeks of blinded follow-up in the HVTN 702 trial’s combined control and vaccine female recipients who were enrolled at overlapping sites with HVTN 703/HPTN 081. We will refer to these as the restricted and enriched control groups, respectively, in HVTN 703/HPTN 081.

In each AMP trial, the estimation will be carried out separately in the control (restricted and enriched for HVTN 703/HPTN 081) and pooled VRC01 groups, i.e., the estimators will be trained separately on data from participants in the control and pooled VRC01 groups (estimation in individual VRC01 dose groups is not considered due to potential convergence failures and limited precision). The best-performing estimator  $\widehat{\psi}_z$  for  $\psi_{0,z}$  will also be identified independently for each  $z \in \{\text{control, pooled VRC01}\}$  in each trial. For the control-group prediction in HVTN 703/HPTN 081, the candidate estimators including the superlearner trained on the restricted control-group data and the candidate estimators including the superlearner trained on the enriched control-group data will be all evaluated together for prediction accuracy, identifying a single best-performing estimator across both the restricted and enriched control-group data sets. For the  $i$ -th enrolled participant with a baseline covariate vector  $W_i$ , the predicted HIV-1 risk score is then defined as the ordered pair  $\left(\widehat{\psi}_{\text{control}}(W_i), \widehat{\psi}_{\text{pooledVRC01}}(W_i)\right)$  of the best-performing estimators.

In more detail, within each combination of trial and treatment stratum, a set of candidate estimators  $\{\widehat{\psi}_1, \dots, \widehat{\psi}_K\}$ , specified in Table 5 in the KwaZulu-Natal risk prediction SAP, and a superlearner estimator  $\widehat{\psi}_{SL}$  for  $\psi_{0,z}$  will first be constructed following Algorithm 1 below. The best-performing estimator  $\widehat{\psi}_z$  is defined as an estimator from the set  $\{\widehat{\psi}_1, \dots, \widehat{\psi}_K, \widehat{\psi}_{SL}\}$  with maximal cross-validated AUC in the treatment stratum  $Z = z$  (see Algorithm 2 below). Following identification of the best-performing estimator in each treatment stratum, we will compute the estimated/predicted HIV-1 risk score for all enrolled participants.

The covariate vector  $W$  will consist of participant-level baseline demographic characteristics and baseline behavioral survey responses. The baseline demographic characteristics include clinical site, country of residence, race, ethnicity, and age in both trials, and, in addition, gender identity in HVTN 704/HPTN 085. The behavioral risk survey consists of 88 questions that aim to assess the risk of HIV infection and can be previewed in Appendix B. HVTN 703/HPTN 081 participants enrolled at clinical sites outside of South Africa were administered an abbreviated form of the behavioral survey consisting of a subset of 60 questions (Appendix C). In order to maximize the use of covariate information, missing responses in the full set of survey questions selected for inclusion in  $W$  (a subset of the 88 questions) will be imputed using the `missForest` method (Stekhoven and Bühlmann, 2011), implemented in the `missForest` R function, for participants outside of South Africa using observed responses from participants enrolled in South Africa. The `missForest` method uses random forests to multiply impute mixed-type data. This method does not require tuning parameters or distributional assumptions and has been shown to perform comparably to or better than other commonly used multiple imputation methods such as multivariate imputation by chained equations or  $k$ -nearest neighbors. Since this analysis considers a large fraction of imputed responses for some behavioral risk variables, another set of superlearner estimators will be fit using only the abbreviated survey, and the best-fitting model will be identified from the pooled set of estimators based on the full/imputed and the abbreviated behavioral risk covariate vectors in this trial.

The risk score computation involves the following steps: Initially, baseline variables with a

large portion of missing responses or sparse response levels will be excluded upfront from the input covariate data set, and for a given  $\widehat{\psi}_z(W)$ , only a subset of the 88 behavioral survey variables and the aforementioned demographic variables will be included in  $W$ . Then, the missForest method will be used to multiply impute missing covariate values in  $W$ . Next, to accommodate a high-dimensional  $W$ , dimension-reducing screening methods will be used for “classical” algorithms. Modified versions of screening methods in SuperLearner’s R functions `screen.glmnet` and `screen.randomforest` for the time-to-event outcome will be used as two screening algorithms combined with each prediction algorithm. More specifically, a Cox model with lasso penalty will be used in `screen.glmnet`, and a survival forest (R function `rsfc`) will be used in `screen.randomforest`. In `screen.randomforest`, the top 20 variables with the greatest variable importance index will be screened in. Lastly, the estimators will be trained using the screened-in covariates, the prediction accuracy will be evaluated, and the best-performing estimators will be used for predicting HIV-1 risk in each treatment stratum.

For the HVTN 703/HPTN 081 enriched control-group candidate estimators,  $W$  will consist of the baseline demographic characteristics specified above and the questionnaire data from the HVTN 702 behavioral risk assessment. The HVTN 702 behavioral risk assessment consists of 23 questions which, like the HVTN 703/HPTN 081 behavioral risk survey, aim to assess risk of HIV infection. Some questions in the HVTN 702 assessment correspond, in part, to questions in the full HVTN 703/HPTN 081 survey but are structured differently. Questions between the two assessments which capture similar information (e.g., number of sex partners) will be consolidated into a single feature where possible. Survey items in the HVTN 702 survey that were not included in the full HVTN 703/HPTN 081 survey (e.g., age at sexual debut) will be multiply imputed using the missForest method. No other covariates from the full HVTN 703/HPTN 081 survey will be used in fitting the enriched control-group candidate estimators. Note that imputation of the enriched data set will be performed separately from the imputation of the restricted HVTN 703/HPTN 081 survey described above. Since this analysis considers a large fraction of imputed responses, another set of candidate estimators will be fit using only the questions that are shared between the HVTN 702 and the full HVTN 703/HPTN 081 surveys. The best-fitting estimator will be identified from the pooled set of estimators based on the complete/imputed and the restricted/enriched control-group data sets in HVTN 703/HPTN 081.

Internal validation of  $\widehat{\psi}_z(W)$  (see Algorithm 2 below) will be based on cross-validated predictions using only data from the AMP trials (with no additional external training set to train the learners). External validation will not be performed. Computation time of `survtmle` scales with the resolution of  $T$ . To limit computation time, person-time will be rounded up to the nearest month.

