9.6 ARV detection

A direct, biomedical measure is used to assess ARV use in this study. This approach is used because self-report of ARV use for PrEP or PEP and other purposes has been shown to be unreliable in a variety of settings [134-136]. For this study, ARV testing will be performed using a test that measures the amount of tenofovir-diphosphate (a metabolite of tenofovir) in red blood cells. This test utilizes a dried blood spot as the sample source and analyzes for tenofovir diphosphate by liquid chromatography and tandem mass-spectroscopy, as previously described [137,138]. Because of a long half-life, high amounts of the metabolite in the dried blood spot correspond with consistent dosing of Truvada and low amounts correspond with inconsistent dosing [76].

Dried blood spot samples are collected from all participants at all scheduled study visits. Periodically, a subset of participant samples will be tested in a manner that will provide an estimate of PrEP use across clinical sites. Storage of dried blood spots as well as serum and plasma (see Appendix F and Appendix I) will allow additional assessment of PrEP use if warranted. Individual test results will not be returned to study sites or study participants.

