## 8.1 Primary Analysis of Prevention Efficacy

The time between enrollment and the date of HIV-1 infection diagnosis determined according to Section 5.3 is evaluated in the MITT cohort. The failure times of participants never observed to be diagnosed with HIV-1 infection are right-censored at the date of the last HIV-negative test or the Week 80 visit, whichever occurs earlier.

Let PE denote the overall prevention efficacy by the Week 80 visit of the 10 mg/kg and 30 mg/kg mAb groups pooled together compared to the control group. We define the primary PE parameter as

$$PE = \{1 - \text{cumulative incidence ratio (pooled mAb groups/control group)} \\ \text{of the primary efficacy endpoint by the Week 80 visit}\} \times 100\%, \quad (1)$$

where the cumulative incidence ratio is the probability of the primary efficacy endpoint by the Week 80 visit for participants assigned to receive the mAb divided by the probability of the primary efficacy endpoint by the Week 80 visit for participants assigned to receive control. More specifically, the primary PE parameter,  $PE(t)$ , will be estimated at a fixed time point  $t$  chosen to be the latest possible time point when stable estimation using follow-up data through the Week 80 visit can be achieved; this is operationalized by defining  $t$  as the maximum time point with 150 participants at risk for the primary endpoint in each of the placebo and individual VRC01 groups. All times-to-event will be right-censored at the Week 80 visit or earlier following the operational rules summarized in Table 1. Note that the fixed time point  $t$  will likely differ for the two AMP trials given the dynamic visit windows. By definition of the stratified estimator, the trial-pooled analysis will use the smaller of the two fixed time points  $t$ . Additionally, note that, due to differences between Schedules 1 and 4, the operational rules in Table 1 imply that an infection endpoint observed in Schedule 4 after the hypothetical Schedule 4 Week 80 visit would be excluded from primary endpoints,

Table 1: Operational rules for right-censoring of times-to-event at the Week 80 visit

HIV status	Visit attendance scenario		Censoring rule	
HIV-Uninfected	Attended s1 wk 80 visit		Censor at s1 wk 80 sample draw date	
	Missed s1 wk 80 visit	Attended s1 post-wk 80 visit	Censor at target s1 wk 80 visit date	
		Attended s4 post-wk 80 visit	Censor at maximum of (hypothetical s4 wk 80 visit  , last s1 sample draw date)	

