### **9.3 Monitoring of the Use of PrEP**

The use of oral FTC/TDF as PrEP (either off-study or provided in the study) may impact study outcomes (e.g., by lowering HIV-1 incidence rendering a loss of study power). Dried blood spot (DBS) samples will be used for assessment of quantitative concentrations of intracellular TFV-DP.

Prevalence of oral FTC/TDF will be reported both as any detectable use and estimated effective use. Estimated percentages of person-years at-risk during any detectable FTC/TDF use and during inferred effective FTC/TDF use will be reported. We summarize how inferred effective use is measured. Current knowledge about PrEP in MSM indicates consistent use of at least 4 doses a week is required to achieve substantial levels of protection. The lower quartile of simulated tenofovir diphosphate (TFV-DP) levels in DBS at 4 doses per week is 719 fmol/punch (Castillo-Mancilla et al., 2013). In iPrEx OLE, the protective levels of TFV-DP in DBS were quantified as 700 fmol/punch (Grant et al., 2014), that is, there were no infections at visits where TFV-DP concentration was 700 fmol per punch or greater. Current knowledge about PrEP in women indicates consistent use of 6–7 doses a week is required to

achieve protection. The lower quartile of simulated TFV-DP levels in DBS at 6 doses per week is 1064 fmol/punch (Castillo-Mancilla et al., 2013). In the HVTN 704/HPTN 085 study we will use 700 fmol/punch as the cut-off to define effective PrEP use based on the lower quartile cited above. For the HVTN 703/HPTN 081 study we will use 1,000 fmol/punch since current knowledge suggests that at least 6 doses of PrEP per week is required for effective PrEP use in women based similarly on the lower quartile. Ongoing work with calibration of DBS from directly observed dosing studies may refine these thresholds. PrEP use measures will be reported by arm to the DSMB; in addition both the OC and the protocol team leadership will see pooled estimates of FTC/TDF use.

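### The SAP's off-PrEP efficacy analysis filters infections but not uninfected follow-up, so its relative PE relies on an unstated equal-use assumption and its absolute outputs are not off-PrEP risks

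*SAP*

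**What the plan says.** SAP 8.5 covers exploratory objective 2 in three steps.

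- **Baseline subgroups.** If baseline PrEP detection is substantial, "the Cox model will be used to assess whether prevention efficacy significantly differs in subgroups with detectable versus undetectable baseline PrEP use", with inference in each subgroup.
- **PrEP during the study.** If use over the trial is substantial, "a marginal structural Cox model will be used to assess prevention efficacy in the sub-population not using PrEP". The text then moves, as if giving the detail of that model, to a repeat of the primary analysis that includes "only MITT infection endpoints with no evidence of PrEP use at the time of HIV-1 diagnosis and at the time of the earliest evidence" (that is, the first sign that the participant was infected). The marker is intracellular tenofovir (TFV) below the lower limit of detection.
- **Optional extra step.** This also excludes cases with self-reported antiretroviral use in the previous 30 days. The reason given begins "Since the ARVs are only detectable in plasma for roughly 14 days".

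The section closes with "These analyses will evaluate uninfected participants without accounting for data on their TFV concentrations".

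The primary analysis being repeated (SAP 8.1) reports one minus a ratio of cumulative incidences. It also reports arm-specific cumulative incidence curves and a control-minus-VRC01 difference, which SAP 8.1 interprets as a probability of infection averted.

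**The concern.** The filter acts on the numerator only. Infections on PrEP are removed, while uninfected person-time on PrEP stays in the risk set. Three problems follow.

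1. PrEP is chosen after randomisation. If the arms differ in PrEP time, the difference enters the PE estimate directly as apparent efficacy or harm. SAP 8.5 neither states nor checks that use is equal.
2. The incidence curves and the additive difference have the wrong denominator for an off-PrEP risk, whether or not use is balanced.
3. A marginal structural model needs PrEP status over time in non-cases, and the procedure offered as its detail does not use it. An analyst cannot tell which analysis is planned.

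PrEP is the co-intervention expected to lower incidence most, so whether VRC01 works without it is a question readers will bring to this section.

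**Working it through.** **The plan's own figure.** Protocol 4.6.3 takes 3.0% annual incidence off PrEP, 90% PrEP efficacy and 50% of person-years on PrEP: (3.0% + 0.3%)/2 = 1.65%, as stated. It gives 78% power for PE = 60%. Expected events per arm are n·λ/(λ+δ)·[1 − exp(−(λ+δ)τ)], with δ = 0.10 a year and τ = 80/52 years.

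- Control: n = 900, λ = 0.0165, giving 20.9 events.
- mAb: n = 1800, λ = 0.0066, giving 16.9 events.
- SE of the log ratio: √(1/20.9 + 1/16.9) = 0.327.
- Power: Φ(0.916/0.327 − 1.96) = 79.9%, close to the stated 78%. The inputs are therefore read correctly.

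**Target quantities off PrEP.** With λ = 0.03 and a hazard-scale PE of 60%:

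- Control: 1 − exp(−0.03 × 80/52) = 4.51%.
- mAb: 1 − exp(−0.012 × 80/52) = 1.83%.
- PE = 59.4%; difference = 2.68 points.

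**What the filter returns.** Let f be an arm's share of person-time on PrEP. If participants move on and off PrEP, the filtered cumulative incidence is 1 − exp(−λ(1−f)τ), so approximately

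PE(filtered) ≈ 1 − (1 − PE)·(1 − f_mAb)/(1 − f_control).

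The off-PrEP share cancels only if f is the same in both arms. The shares below are assumptions; 50% is the Protocol 4.6.3 scenario.

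| f control | f mAb | PE read, true hazard PE 60% | PE read, true PE 0% |
|---|---|---|---|
| 50% | 50% | 59.7% | 0% |
| 50% | 55% | 63.7% | +9.9% |
| 50% | 45% | 55.7% | −9.9% |
| 50% | 60% | about 68% | +19.8% |
| 50% | 40% | about 52% | −19.7% |

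Equal use of 25% to 75% gives 59.6% to 59.9%. Simulations with equal 50% use, 1.5 million per arm, varied four things: persistent or switching use, exclusion or censoring of filtered cases, PrEP users at twice the risk, and PE on PrEP of 0%, 60% or 90%. The filtered and true off-PrEP PE differed by at most 0.5 point.

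**Absolute outputs with equal 50% use.** Control risk reads 1 − exp(−0.015 × 80/52) = 2.28% instead of 4.51%. The risk difference reads 1.36 points instead of 2.68. If use is persistent, so that half the people are always on PrEP, the figures are 0.5 × 4.51% = 2.26% and 0.5 × 2.68 = 1.34 points.

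**How large an imbalance chance allows.** Treating use as persistent, with 900 against 1800 participants, the SE of the arm difference is √(0.25 × (1/900 + 1/1800)) = 2.0 points at 50% use and √(0.21 × (1/900 + 1/1800)) = 1.9 points at 30%. At 50% use a 5-point gap is about 2.4 SE and a 10-point gap about 4.9 SE.

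**The optional step.** Its rationale is a plasma window. The marker named in SAP 8.5 is intracellular TFV, which SAP 9.3 and Protocol 9.6 measure as TFV-DP in dried blood spots (DBS); Protocol 9.6 attributes a long half-life to it. The same section says "self-report of ARV use for PrEP or PEP and other purposes has been shown to be unreliable". The step again filters cases only.

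**The case against.** The best defence is that PE is a ratio in a randomised trial. Participants and site staff are blinded (Protocol 4.12) and every arm gets the same prevention package (Protocol 2.5), so PrEP use should be similar by arm and the on-PrEP follow-up cancels. This stands, and the equal-use results above confirm it. A reader might infer that the analysis cannot estimate efficacy off PrEP at all. The documents do not support that reading.

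A reader might also infer that use will differ by arm because participants are asked which product they think they received (SAP Appendix B, item 86). That question records belief. It is not evidence of unblinding or of unequal PrEP use, and imbalances of 5 to 10 points lie well outside typical chance variation.

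Further points on the other side:

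- The baseline-PrEP Cox analysis treats cases and non-cases alike, on a pre-treatment variable. It is sound, though it does not address uptake after enrolment.
- The closing sentence of SAP 8.5 may refer only to the two filtered analyses, leaving the marginal structural model open, and DBS are stored at every visit. Even so, the section then gives that model no specification at all.
- The filtered curves are valid as incidence of infection without detectable PrEP among everyone analysed. That is a matter of labelling, and SAP 8.5 does not supply the label.
- Appendix F of the protocol does schedule antiretroviral detection in serum or plasma, the self-report step is optional, and a long half-life makes a below-limit DBS result stronger evidence of no recent use. These points soften the criticism of the optional step, but its stated reason still does not match the assay.

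**Conclusion.** The concern holds in limited form. The filtered analysis gives a nearly unbiased relative PE off PrEP provided PrEP use is equal by arm over time. That is plausible, but the SAP neither states nor checks it. With control at 50% PrEP time, each 5-point difference shifts PE by about 4 points at a true PE of 60%, and by about 10 points at a true PE of zero. These are sensitivity figures on assumed shares and do not predict an imbalance.

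The arm-specific incidences and the additive difference are not off-PrEP quantities even with perfect balance; at 50% PrEP time they are about half the off-PrEP values. The marginal structural model is named but not specified.

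The objective is exploratory and the analysis depends on substantial PrEP use. The primary PE deliberately averages over PrEP choice (Protocol 4.2.1) and is unaffected.

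**What to change.** In SAP 8.5:

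1. Keep the filtered analysis, labelled as PE against infection without detectable PrEP in all MITT participants as randomised. State the equal-use assumption and show percent person-years on detectable PrEP by arm beside the result. SAP 9.3 already estimates this quantity and says "PrEP use measures will be reported by arm to the DSMB". Do not present the incidence or additive outputs as off-PrEP risk.
2. Add an analysis dividing each arm's off-PrEP infections by its estimated off-PrEP person-years: at-risk person-years × (1 − estimated share on detectable PrEP in that arm), with a participant bootstrap CI. Use one threshold throughout, since SAP 8.5 refers to the limit of detection and SAP 9.3 to the limit of quantitation. Restrict infections and person-time to the period with DBS storage: the SAP 9.3.1 simulation starts collection on 1 November 2016, and Protocol Section 1 implies earlier enrolment. Note that this analysis still conditions on PrEP choice made after randomisation.
3. Run the marginal structural Cox model only with TFV-DP from a sample of non-cases, entered by inverse-probability weights. Otherwise remove it.
4. Replace the 14-day plasma rationale with one that fits DBS TFV-DP, and treat the self-report exclusion as a sensitivity check only.

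**Cost.** SAP wording and modest programming. Items 1, 2 and 4 need no new visits, and item 2 can use the DBS samples already assayed for monitoring; item 3 may need extra assays on stored samples. The CI for item 2 widens slightly. Assuming 500 independent assays split 1:2, the estimated share adds an SE of √[f/(1−f) × (1/167 + 1/333)] on the log scale, which is 0.06 at f = 30% and 0.09 at 50%. With about 19 and 15 off-PrEP infections (0.015 and 0.006 a year in the event formula above), the infection SE is 0.34, so the interval widens by about 2% to 4%.
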